11.2.2 Serious Adverse Events (SAEs)

11.2.2.1 Site Requirements for Reporting SAEs to HCRN

- SAEs will be reported from time of signed informed consent until 90 days after discontinuation of study drug(s).
- SAEs will be reported on the SAE Submission Form **within 1 business day** of discovery of the event.
- SAEs include events related and unrelated to the study drug(s).
- All SAEs will be recorded in the subject's medical record and on the appropriate study specific eCRF form within the EDC system.
- All SAEs regardless of relation to study drug will be followed until resolution to \leq Grade 1 or baseline and/or deemed clinically insignificant and/or until a new anti-cancer treatment starts, whichever occurs first.

The site will submit the completed SAE Submission Form to HCRN **within 1 business day** of discovery of the event. The form may be submitted to HCRN electronically to [contact]. The site investigator is responsible for informing the IRB and/or other local regulatory bodies as per local requirements.

The original copy of the SAE Submission Form and the email correspondence must be kept within the study file at the study site.

Once the SAE has resolved (see resolution guidelines listed in 11.2.2.1), sites must submit a follow-up SAE Submission Form within a reasonable timeframe to HCRN electronically to [contact].

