6.3 Subject Withdrawal/Protocol Therapy Discontinuation

Subjects may withdraw consent at any time for any reason or be dropped from the trial at the discretion of the site investigator should any untoward effect occur. In addition, a subject may be withdrawn by the site investigator or the sponsor-investigator if enrollment into the trial is inappropriate, the trial plan is violated, or for administrative and/or other safety reasons.

A subject must be discontinued from the trial for any of the following reasons:

- The subject or legal representative (such as a parent or legal guardian) withdraws consent.
- Confirmed radiographic disease progression
NOTE: A subject may be granted an exception to continue on treatment with confirmed radiographic progression if there is objective clinical benefit, please see Section 5.3
- Unacceptable adverse experienced
- Intercurrent illness that prevents further administration of treatment
- Site investigator's decision to withdraw the subject
- The subject has a confirmed positive serum pregnancy test
- Noncompliance with trial treatment or procedure requirements
- The subject is lost to follow-up
- Protocol therapy interrupted for > 12 weeks
- Completed 24 months of uninterrupted treatment with pembrolizumab or 35 administrations of pembrolizumab, whichever is later. **NOTE:** 24 months of pembrolizumab is calculated from the date of first dose.
- Administrative reasons

The End of Treatment and Follow-up visit procedures are listed in Section 7. After the end of treatment, each subject will have follow up visit (1) at 30 days after last dose of study treatment. Serious adverse events will be collected for 90 days after last dose of study treatment (follow up visit 2). Follow up for patients that have not experienced progression will occur every 9 weeks \pm 7 days. This may be done by phone call or other avenues as appropriate. Every effort should be made to obtain information on radiology scans or other types of disease assessment documentation. Once a subject experiences confirmed disease progression or starts a new anti-cancer therapy, the subject moves into the survival follow-up phase and should be contacted by telephone every 12 weeks \pm 7 days to assess for survival status until death, withdrawal of consent, or the end of the study, whichever occurs first.

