¹¹ An end of treatment (EOT) visit will be performed for the following situations: (1) if patient has progressed and a discussion of scans/next treatment is needed or (2) if a patient has experienced toxicities that necessitates study treatment discontinuation. Special attention should be given to the assessment of current depression, suicidal tendencies or relapse of substance abuse. If concerns are identified during this visit, the appropriate referral to psychiatric services should be made to further assess. There may be certain situations in which this visit will take place locally and discussion regarding next steps would occur via phone call. In this case the research specific blood samples would not be done until the safety follow up visit.

¹² A safety follow up visit will be performed about 4 weeks after the EOT visit or last dose of study drug. Special attention should be given to the assessment of current depression or suicidal tendencies in addition to relapse of substance abuse. If concerns are identified during this visit, the appropriate referral to psychiatric services should be made to further assess. After completion of the EOT visit, subjects should be contacted on a monthly basis until 180 days after their last dose of study drug to assess for issues with mood or behavior. If a concern is identified the patient will be referred to the appropriate mental health resources for evaluation. If research specific blood samples were not done during the EOT visit, they should be drawn during this visit. This visit may take place locally if the patient had an EOT visit at the study facility and study specific blood samples were drawn at that time.

¹³ Long Term Follow up will occur every 12 weeks \pm 7 days. This may be done by phone call or other avenues as appropriate. Every effort should be made to obtain information on radiology scans or other types of disease assessment documentation. Follow up will continue until death, withdrawal of consent, or the end of the study, whichever occurs first.

Hematology	Chemistry	Urinalysis	Other
Hematocrit	Albumin	Blood	Serum β -human chorionic gonadotropin [†]
Hemoglobin	Alkaline phosphatase	Glucose	(β -hCG) [†]
Platelet count	Alanine aminotransferase (ALT)	Protein	PT (INR)
WBC (total and differential)	Aspartate aminotransferase (AST)	Specific gravity	aPTT
Red Blood Cell Count	Total protein	Microscopic exam (If abnormal)	Total triiodothyronine (T3)

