11.2 Reporting

11.2.1 Adverse Events

- AEs will be recorded from time of signed informed consent until 30 days after discontinuation of study drug(s).
- AEs will be recorded regardless of whether or not they are considered related to the study drug(s).
- All AEs will be recorded in the subject's medical record and on the appropriate study specific eCRF form within the EDC system.
- AEs considered related to study drug(s) will be followed until resolution to \leq Grade 1 or baseline, deemed clinically insignificant, and/or until a new anti-cancer treatment starts, whichever occurs first.

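### Mood contacts run to day 180, but new psychiatric events after day 30 (non-serious) or day 90 (serious, non-fatal) have no stated route into the safety data

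*Combined protocol and SAP*

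**What the plan says.** Three time limits apply after treatment ends.

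- **Mood and behaviour contacts, to day 180.** Under Section 7, footnote 12, once the end-of-treatment visit is done subjects are to be "contacted on a monthly basis until 180 days after their last dose of study drug to assess for issues with mood or behavior". The stated consequence is: "If a concern is identified the patient will be referred to the appropriate mental health resources for evaluation". No AE form, SAE form or case report form entry is mentioned.
- **AE recording, to day 30.** Section 11.2.1: "AEs will be recorded from time of signed informed consent until 30 days after discontinuation of study drug(s"). This applies whether or not the event is thought related to treatment.
- **SAE reporting, to day 90.** Section 11.2.2.1 has SAEs reported from consent "until 90 days after discontinuation of study drug(s"), again regardless of relatedness. Section 6.3 agrees: "Serious adverse events will be collected for 90 days after last dose of study treatment (follow up visit 2").

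Some events already on record stay open for longer. Section 11.2.1 says: "AEs considered related to study drug(s) will be followed until resolution to" Grade 1 or baseline, subject to other end points that include the start of a new anti-cancer treatment. Section 11.2.2.1 has a similar rule for all SAEs.

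Section 12.4.2 summarises AEs, SAEs, AEs that lead to stopping treatment, and deaths. Section 13.2 gives the DSMC an AE summary for its quarterly review.

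**The concern.** The protocol itself treats neuropsychiatric toxicity as an important risk. Section 3.2 excludes patients with a history of bipolar disorder or major depression and those with a known serious neuropsychiatric condition. Footnote 2 of the calendar screens for depression and suicidal tendencies at every physical exam. Table 4 lists severe neuropsychiatric toxicity that persists or worsens among the reasons to stop Sylatron for good. Safety and tolerability is a secondary objective (Section 2.1.2).

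The plan therefore looks actively for late mood problems but does not say that what it finds becomes data. Take a non-fatal suicide attempt that first occurs on day 120 and comes to light at a monthly contact. As written, it leads to a referral. It falls outside the stated windows for the AE and SAE records, and so outside the safety summaries and the DSMC's AE summary. It would also miss onward reporting to the drug supplier, because under Section 11.2.2.2 that starts from a site's submission form.

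**Working it through.** The plan states no figure to reproduce. The check sets the windows side by side, looks for another route, and counts.

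**1. Is there another route?** I found none in the protocol text.
- In the Section 7 calendar, the AE row is marked at screening, on treatment, at end of treatment and at the safety visit. It has no mark under long-term follow-up, and the monthly contacts have no column of their own.
- The events of clinical interest in Section 11.6 are a pembrolizumab overdose and a pattern of liver tests. Neither is psychiatric.
- The extended follow-up in Sections 11.2.1 and 11.2.2.1 covers events already recorded, not new ones.
- Survival follow-up (Section 6.3) captures deaths, and Section 12.4.2 counts deaths as a safety parameter.

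**2. How much of the contact period is uncovered?** The documents say only that contacts are monthly. I assume every 30 days from the last dose: 180 / 30 = 6 contacts. I read the windows as applying to the onset of new events.

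| Contact (day) | New non-serious AE | New SAE |
|---|---|---|
| 30 | recorded | reported |
| 60, 90 | no stated route | reported |
| 120, 150, 180 | no stated route | no stated route, unless fatal |

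- Contacts after the AE window: 5 of 6. Contacts after the SAE window: 3 of 6.
- Days outside the AE window: (180 − 30) / 180 = 150 / 180 = 83%.
- Days outside the SAE window: (180 − 90) / 180 = 90 / 180 = 50%.

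The exact contact days could shift. Because contacts begin after the end-of-treatment visit, a late visit would remove early contacts rather than the late, uncovered ones.

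**3. Which drug starts the clock?** The AE and SAE windows run from discontinuation of study drug(s), and the contacts run from the last dose of study drug. Section 5.2 plans Sylatron for up to 12 weeks and lets pembrolizumab continue, so the two drugs can stop at different times.

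As an illustration, suppose all clocks start when the second drug stops, and treatment ends at 24 weeks (the progression-free survival that Section 1.4.4 calls meaningful).
- The last of 12 weekly Sylatron doses falls on day 1 + 11 × 7 = 78.
- Treatment ends on day 24 × 7 = 168.
- AE recording runs to day 168 + 30 = 198, which is 198 − 78 = 120 days after the last Sylatron dose.
- SAE reporting runs to day 168 + 90 = 258, which is 258 − 78 = 180 days after it.

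A patient who stops both drugs together has only 30 and 90 days of capture after interferon. In both cases the contacts outlast the windows by 150 and 90 days on a common clock.

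**The case against.** The strongest reply is that footnote 12 is there to protect patients, not to collect data. Welfare contacts may reasonably outlast the reporting windows, and the 90-day SAE limit is stated consistently in two sections. The safety analysis is descriptive and single-arm, and no planned analysis estimates late psychiatric incidence. By days 120 to 180 many patients may have progressed or started other treatment, which makes attribution weak: the second-line FOLFOX4 series in Section 1.1.1 had a median survival of 138 days. Extending collection for one class of event also makes ascertainment uneven. Finally, AE and SAE forms sit in the Study Procedures Manual or the data capture system (Section 11), and footnote 1 refers to that manual for more on psychiatric assessment. It may say how contact findings are documented.

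Much of this stands, and it limits the size of the point. It does not close the gap, because the protocol text that defines the windows does not say where findings at the contacts go.

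A reader might infer that psychiatric events found at these contacts never enter the safety data. The documents do not support that. AEs to day 30 and SAEs to day 90 are captured whatever their cause, related AEs and all SAEs already on record are followed further, and deaths are counted. A reader might also infer that a planned estimate of late psychiatric toxicity is biased towards zero. No such estimate is planned; what is affected is the completeness of a descriptive summary.

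**Conclusion.** The mismatch holds in a limited form. New non-serious psychiatric events after day 30, and new serious non-fatal ones after day 90, have no stated route into the safety dataset, the summaries or the DSMC reports, although the protocol looks for them to day 180. On a 30-day contact schedule this affects five of six contacts for AEs and three of six for SAEs. It rests on that assumed spacing, on one common clock, and on the protocol text without the procedures manual. For patients who stay on pembrolizumab after Sylatron, the uncovered period after interferon shrinks if the clock starts with the last dose of either drug.

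The number of events lost cannot be estimated from the documents. A reader might take the 17% depression figure in Section 1.3.2 as a guide, but it describes reactions present when treatment was stopped, and such events would fall inside this trial's AE window. It also comes from adjuvant melanoma treatment lasting up to five years, whereas the same section puts this trial's total Sylatron dose at under 20% of that study's median. It should not be used as a measure of size.

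The change is worth making because it is cheap and alters what the safety dataset and the DSMC see.

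**What to change.** - In Sections 11.2.1 and 11.2.2.1, state that neuropsychiatric AEs and SAEs identified at the monthly contacts are recorded and reported through 180 days after the last dose, and are included in the safety summaries (Section 12.4.2) and the DSMC reports (Section 13.2).
- Cross-refer to this from footnote 12, and give the contacts a place on the case report form.
- State which drug's last dose starts the 30-, 90- and 180-day clocks, and use the same term in Sections 6.3, 7 and 11.2.

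The contacts already take place, so no visit is added and clinical care does not change. The costs are protocol and case report form wording, modest extra data entry, and SAE reporting within one business day over a longer period. Psychiatric events would then have a longer collection window than other events, and attribution is weaker once new therapy starts. Both points should be noted wherever the late events are tabulated, for example by showing them separately from events within the standard windows.

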11.2.2.2 HCRN Requirements for Reporting SAEs to Merck

Hoosier Cancer Research Network will report any possibly related and unexpected SAE to Merck **within one business day** of receipt of the SAE/ECI Submission Form and to regulatory authorities (FDA) per federal guidelines. Follow-up information will be provided to Merck as it is received from site. Merck Global Safety. (Attn: Worldwide Product Safety; [contact]).

11.2.2.3 Sponsor-Investigator Responsibilities

HCRN will send a SAE summary to the sponsor-investigator **within 1 business day** of receipt of SAE Submission Form from a site. The sponsor-investigator will promptly review the SAE summary and assess for expectedness and relatedness.

11.3 HCRN Responsibilities to FDA

HCRN will manage the Investigational New Drug Application (IND) associated with this protocol on behalf of the sponsor-investigator. HCRN will cross-reference this submission to the Merck's parent IND at the time of submission. Additionally, HCRN will submit a copy of these documents to Merck at the time of submission to FDA.

For protocols conducted under an IND, HCRN will be responsible for all communication with the FDA in accordance with 21CFR312 including but not limited to the 7 and 15 Day Reports, as well as an Annual Progress Report. Additionally, HCRN will submit a copy of these reports to Merck at the time of submission to FDA.

11.4 IND Safety Reports Unrelated to this Trial

Merck will provide to HCRN IND safety reports from external studies that involve the study drug(s) per their guidelines. HCRN will forward safety reports to the sponsor-investigator who will review these reports and determine if revisions are needed to the protocol or consent. HCRN will forward these reports to participating sites **within 1 business day** of receiving the sponsor-investigator's review. Based on the sponsor-investigator's review, applicable changes will be made to the protocol and informed consent document (if required). All IND safety reports will also be made available to sites via the EDC system.

Upon receipt from HCRN, site investigators (or designees) are responsible for submitting these safety reports to their respective IRBs, as per their IRB policies.

11.5 Reporting of Pregnancy and Lactation to the Sponsor-Investigator and to Merck

Although pregnancy and lactation are not considered adverse events, it is the responsibility of site investigators or their designees to report any pregnancy or lactation in a subject (spontaneously reported to them), including the pregnancy of a male subject's female partner that occurs during the trial or within 120 days of completing the trial. All subjects and female partners of male subjects who become pregnant must be followed to the completion/termination of the pregnancy. Pregnancy outcomes of spontaneous abortion, missed abortion, benign hydatidiform mole, blighted ovum, fetal death, intrauterine death, miscarriage, and stillbirth must be reported as serious adverse events. If the pregnancy continues to term, the outcome (health of infant) must also be reported.

Such events must be reported **within 24 hours** to HCRN. HCRN will report such events to the sponsor-investigator and Merck Global Safety **within 1 business day** of receiving notification of the event. (Attn: Worldwide Product Safety; [contact])

11.6 Events of Clinical Interest

Events of Clinical Interest (ECI) described below must be recorded as such on the SAE/ECI Submission Form and reported **within 24 hours** to [contact] at HCRN. HCRN will report these events within **one business day** of receipt to Merck Global Safety. (Attn: Worldwide Product Safety; [contact]).

Events of clinical interest for this trial include:

1. an overdose of Funder's product that is not associated with clinical symptoms or abnormal laboratory results. For purposes of this trial, an overdose will be defined as any dose exceeding the prescribed dose for pembrolizumab greater than 10mg/kg over the prescribed dose. No specific information is available on the treatment of overdose of pembrolizumab. In the event of overdose, pembrolizumab should be discontinued and the subject should be observed closely for signs of toxicity. Appropriate supportive treatment should be provided if clinically indicated. If an adverse event(s) is associated with ("results from") the overdose of a Merck product, the adverse event(s) is reported as a serious adverse event, even if no other seriousness criteria are met.
2. an elevated AST or ALT lab value that is greater than or equal to 3X the upper limit of normal and an elevated total bilirubin lab value that is greater than or equal to 2X the upper limit of normal and, at the same time, an alkaline phosphatase lab value that is less than 2X the upper limit of normal, as determined by way of protocol-specified laboratory testing or unscheduled laboratory testing.*

***NOTE:** These criteria are based upon available regulatory guidance. The purpose of the criteria is to specify a threshold of abnormal hepatic tests that may require an additional evaluation for an underlying etiology.

12 STATISTICAL METHODS

12.1 Study Design

This is an open-label, single-arm, multicenter Phase II safety and efficacy study of combination therapy with pembrolizumab and Sylatron (Peginterferon alpha-2b) in patients with advanced cholangiocarcinoma who have progressed on or cannot tolerate frontline chemotherapy.

12.2 Endpoints

12.2.1 Definition of Primary Endpoint

- Efficacy endpoint: objective response rate: defined as the proportion of subjects who achieve the best response (CR and PR) determined by RECIST1.1.

12.2.2 Definition of Secondary Endpoints

- PFS: defined as time from registration till the patient's disease progression or death from any cause whichever occurs first (those for whom event of progression or death not observed will be censored).
- OS: defined as time from registration till the patient's death from any cause (patient who are still alive at the end of the study will be censored).

- Objective response rate: defined as the proportion of subjects who achieve the best response (CR and PR) determined by irRECIST.
- Safety and tolerability of the combination of Sylatron and pembrolizumab as assessed by CTCAE v4. Will include patients' toxicity profile, adverse event, serious adverse event, serious adverse even leading to discontinuation of the treatment, death.

12.2.3 Definition of Exploratory Endpoints

- The density of CD3 and CD8 in the tumor interior and invasive margin of the tumor, and the clonality of the T-cell repertoire.
- Proliferation of CD8+ T cells, Granzyme B+ cells and proliferation of tumor cells.

12.3 Sample Size and Accrual

The primary objective of the study is to test that addition of Sylatron will improved the response rate of pembrolizumab from 17% to 35% in patients with advanced cholangiocarcinoma. The sample size is based on the number of patients that are anticipated to complete the primary objective.

We propose that the addition of Sylatron to a pembrolizumab regimen will improve the response rate of pembrolizumab from 17% to 35%. Simon's two-stage optimum design will be used to test the null hypothesis of $P \leq 0.17$ versus the alternative hypothesis of $P \geq 0.350$. At the first stage, 16 patients will be treated with the combination of Sylatron and pembrolizumab. The trial will be terminated if 3 or fewer respond. If there are at least 4 responders, the trial will go on to the second stage and 28 patients will be enrolled to a total of 44 patients. If the total number responding among the 44 patients is less than or equal to 11, the null hypothesis will not be rejected and the combination of Sylatron plus pembrolizumab will not be investigated further. Using this statistical method, there is a 0.046 (4.6%) probability of erroneously concluding that this drug combination is effective when it actually is not (targeted value of 0.05). If the drug is actually effective, there is a 0.191 (19.1%) probability of concluding that it is not (targeted value of 0.2). The power of the design is 80% with a one-sided significance level of 0.05.

We anticipate that 2 patients will be recruited per month and total time for study recruitment will be 24 months, with each patient followed for a minimum of 6 months, the anticipated time to complete the study will be 24 – 30 months. Allowing for a 4% drop out rate, a total of 46 patients will be enrolled for this trial.

